Form A

IRB # STU-2022-0768

b. Current practice

[figure not shown]
After discharge, current practice is to transition patients back to a home oral diuretic regimen in hopes that this will provide sufficient diuresis to prevent re-hospitalization.

3. Study Design.

[figure not shown]
Describe the study design (e.g., single/double blind, parallel, crossover, etc.) Consider inserting a scheme to visually present the study design.

This will be a randomized, open-label pilot study of 70 patients with and without diuretic resistance who were recently admitted and discharged for acute decompensated heart failure with an oral diuretic regimen testing whether Furoscix is more effective at achieving post-discharge outpatient diuresis than standard of care.

Schema:

Visual description of the BAN-ADHF Score

Form A

IRB #

STU-2022-0768

4. Research Plan / Description of the Research Methods:**4.a. Provide a comprehensive narrative describing the research methods.**

- 1) Provide the order in which tests/procedures will be performed,
- 2) Provide the setting for these events and a description of the methods used to protect privacy during the study.
- 3) Provide the plan for data analysis (include as applicable the sample size calculation)

Please respond to all components of this item, or clearly indicate which components are not applicable.

Inclusion and Exclusion Criteria:

Eligibility criteria are shown in the following table:

Inclusion Criteria	Exclusion Criteria

 • English speaking patients discharged after ward hospitalization for acute decompensated heart failure • Able to be screened and enrolled within 14 days of discharge • Recent echocardiogram (6 months or less) • Discharged with diuretic therapy 	
 • Chronic kidney disease stage 5 (GFR<20) or End Stage Kidney Disease • Systolic blood pressure <100 • ICU hospitalization within 3 months • Inotrope use within last 3 months • Home inotropes • Electrolyte abnormalities on discharge • Inadequate data for BAN-ADHF score • Pregnant • Prior heart transplantation or left ventricular assist device • Low-output heart failure • Concurrent use of non-loop diuretic • Advanced liver disease • Severe malnutrition • Skin/Soft tissue condition precluding Furoscix • Inability to collect urine • Non-English-speaking patients

Intervention, Setting, and Design: We are recruiting patients from UTSW and Parkland. All of the research procedures in this study will take place at the Clinical Research Unit in the Aston Building at UT Southwestern Medical Center. This will be a randomized, open-label pilot study of 70 patients with and without diuretic resistance who were recently admitted and discharged for acute decompensated heart failure with an oral diuretic regimen testing whether Furoscix is more effective at achieving post-discharge outpatient diuresis than oral diuretics. Diuretic resistance will be identified using the BAN-ADHF (Blood urea nitrogen, creatinine, Natriuretic Peptide levels, Atrial fibrillation, Diastolic blood pressure, Hypertension and Home diuretic dose, and Heart Failure hospitalization) score which has been integrated into the electronic health record. The score is integer-based with a score of ≥ 12 indicating diuretic resistance with high likelihood of poor outcomes.

Screening:

- We are requesting a partial HIPAA waiver to review electronic health records and confirm their eligibility in the study. Pre-screening will occur through the electronic health record to evaluate for inclusion and exclusion criteria and to assess if women of child-bearing potential have a pregnancy test to confirm they are not pregnant. Lab testing will be reviewed. These include review of urine drug screen, alcohol screen (if clinically indicated), NT-proBNP, creatinine clearance.
- BAN-ADHF score will be calculated.

Form A

IRB #

STU-2022-0768

- After patients are screened, patients will be approached for potential participation. If patients are interested, they will be scheduled for an in-person randomization visit optimally within 1-7 days of hospital discharge, although patients will be eligible up to 14 days after discharge.
- At the research appointment, patients will be asked if they are interested in voluntarily participating in this study.

Research Visit:

Pre-Randomization:

- Confirm eligibility
- Obtain informed consent
- Physical exam including vital signs assessment.
- Prior and concomitant medication assessment.

Randomization:

If patients still meet all eligibility criteria and sign informed consent, they will undergo stratified randomization based on BAN-ADHF score (≥ 12 vs. < 12). Within each stratum, patients will be randomized in a 1:1 ratio (intervention: control) during the research visit. Patients will be informed via telephone prior to visit to not take home oral dose of diuretic on the day of the visit and will be instructed to hold any caffeine products such as coffee or any other drugs that could increase urine output on the day of the visit.

- **Intervention: Furoscix** – administration of subcutaneous furosemide (Furoscix) during study visit. It will be administered using the Furoscix Infusor. Per information from the Sponsor, "The Infusor is placed on the patient's abdomen for subcutaneous infusion. Furoscix is delivered subcutaneously through a small, 27-gauge, 6 mm needle. The Infusor is preprogramed to deliver 80 mg (10 mL) furosemide over 5 hours using a biphasic delivery profile of 30 mg furosemide (3.75 mL) over the first hour and 12.5 mg furosemide (1.56 mL) per hour over the subsequent 4 hours."
- **Control: Oral Diuretic** - administration of oral diuretic during study visit. Patients will bring their home prescription of oral diuretic and will take the oral formulation while in the visit. If the patient did not bring their home dose, an equivalent oral dose will be provided from the UT Southwestern Investigational Drug Service.

The intervention arm (Furoscix over 5 hours at 8 mg/mL) will be compared to a usual care group (home oral diuretic dose prescribed by discharge physician). Patients will be monitored for 8 hours in the Clinical Research Unit post-drug administration for clinical safety and to measure clinical response.

Other research procedures:

- Patients will be instructed to void immediately before dosing (pre-dose urine) and this sample will be discarded. After medication administration, urine from spontaneous voids during post-dose phases will be collected and recorded. Urine sodium measurements will be obtained at hourly intervals. Urine from each collection period must be refrigerated until the end of the collection period. Total volume of urine produced will be assessed over 8 hours post-study drug administration. 5 mL of each hourly urine sample will be sent for a urine sodium lab test in a yellow round bottom tube.
- Collect approximately 10 mL of blood for a blood test to check patient's electrolytes. This will be done at the end of the research visit.
- Call participants in 7 days after their research visit to assess if patient has had a presentation to urgent care, emergency department, or is re-hospitalized for acute exacerbation in heart failure.

Compensation:

To account for a full day of research monitoring, patients will be compensated \$250 for their participation in the study with the UTSW ClinCard.

Data Safety and Monitoring:

Patient safety will be tracked over the study. For any adverse events (AE) that occur during their participation in the study, medical care will be provided and patients will be followed until resolution. See Form D for more details.

Form A

IRB #

STU-2022-0768

Privacy and Confidentiality:

To protect patient's privacy and confidentiality, we will ensure the consent process takes place in a private area and conduct research in secure areas where others will not have access to their PHI. All PHI collected during the study will be coded with a Subject ID using a randomized code. The key to the code will be kept on a password database in the research coordinator's locked office. Only authorized personnel listed on Form B will have access to the data. Any hard copy documents such as the signed consent form will be kept in the research coordinator's locked office.

Statistical Analysis:

This study will assess the primary outcomes of greater diuretic efficiency as measured by total urine output and urine sodium. As the Furoscix group will receive 80 mg of subcutaneous furosemide and the control group will take a home dose of oral diuretic, urine output will be normalized per mg of treatment administered. Differences in total urine produced will be compared between Furoscix versus oral diuretic groups. The urine sodium will be assessed hourly, and will be compared across the two groups.

As this study is a preliminary pilot study to assess the effect of Furoscix on diuretic efficacy, we have chosen a convenience sample of 70 patients to allow for a comparison between patients who receive Furoscix and those who do not receive Furoscix. The results of this trial will serve as a precursor for a larger, multicenter trial of Furoscix in patients with diuretic resistance.

4.b. List of the study intervention(s) being tested or evaluated under this protocol

	N/A - this study does not test or evaluate an intervention. Skip to item 4.d.		
#	Study intervention(s) being tested or evaluated under the protocol Add or delete rows as needed	Affiliate Place a check next to institution(s) where the intervention will be performed	Local Standard Practice? Indicate whether the intervention is considered acceptable practice locally for applicable institutions
1	Furoscix (Furosemide subcutaneous)	 UTSW  PHHS  CMC  THR  TSRH  Other: _____	 Yes  Yes  Yes  Yes  Yes  Yes
2	Insert study intervention 2 here	 UTSW  PHHS  CMC  THR  TSRH  Other: _____	 Yes  Yes  Yes  Yes  Yes  Yes

Form A

IRB # STU-2022-0768

4.c. Risk:Benefit Analysis of study interventions being tested or evaluated under this protocol

For each study intervention identified in section 6b above, complete a risk:benefit analysis table.

(Two tables are provided, copy & paste additional tables as needed or delete both tables if this study does not test an intervention)

4.c. Study Intervention #1 Furoscix (Furosemide subcutaneous)	
List each group exposed to this intervention on a separate line. (e.g., experimental, control, Arm A, Arm B, etc) Or state All Groups/Subjects	For each group, list the benefits of this intervention. (Benefits can be directly from the intervention or from a monitoring procedure likely to contribute to the subject's well being). If there are no benefits, state "none".
Intervention arm (Furoscix)	Participants will not personally benefit from this study. Their participation may provide data that will help prevention of future heart failure hospitalizations.

If you are requesting a Waiver of Informed Consent, complete the table below.If you have a consent form, list the reasonably foreseeable **risks** in the consent form (and do not complete this section).

List the risks according to the probability (likely, less likely or rare) and magnitude (serious or not serious).

(include: 1) expected adverse events; 2) rare and serious adverse events; 3) all other psychological, social, legal harms)

Do not delete frequency. Frequency must be estimated because it will assist you with determining which adverse events will require prompt reporting.

	Not serious	Serious
Likely These risks are expected to occur in more than 20 out of 100 subjects.	•	•
Less likely These risks are expected to occur in 5-20 subjects or less out of 100 subjects.	•	•
		Serious
Rare These risks are expected to occur in less than 5 subjects out of 100		•

Form A

IRB #	STU-2022-0768
-------	---------------

4.c.

Study Intervention #1

Insert name used in 4.b.

List each group exposed to this intervention on a separate line. (e.g., experimental, control, Arm A, Arm B, etc) Or state All Groups/Subjects	For each group, list the benefits of this intervention. (Benefits can be directly from the intervention or from a monitoring procedure likely to contribute to the subject's well being). If there are no benefits, state "none".

If you are requesting a Waiver of Informed Consent, complete the table below.

If you have a consent form, list the reasonably foreseeable **risks** in the consent form (and do not complete this section).

List the risks according to the probability (likely, less likely or rare) and magnitude (serious or not serious).

(include: 1) expected adverse events; 2) rare and serious adverse events; 3) all other psychological, social, legal harms)

Do not delete frequency. Frequency must be estimated because it will assist you with determining which adverse events will require prompt reporting.

	Not serious	Serious
Likely These risks are expected to occur in more than 20 out of 100 subjects.	•	•
Less likely These risks are expected to occur in 5-20 subjects or less out of 100 subjects.	•	•
Rare These risks are expected to occur in less than 5 subjects out of 100		•

Form A

IRB #	STU-2022-0768
-------	---------------

		
4.d. List ALL other research procedures or components not listed in table 4.b. The combination of Tables 4b and 4d should account for all of the research procedures that will take place during this study.
 
Consider grouping similar procedures under a single component (e.g., blood work, CT = safety assessments)
		
#	Research component	Column A	Column B	Column D
	
 individual procedures 
example: Eligibility Assessments 
 History and physical Questionnaire Laboratory tests 
 
Add or delete rows as needed
	Local Standard Practice Indicate the number of times each procedure will be performed as stipulated in the research plan that would be performed if the participant were not participating in the study.	Research Only Indicate the number of times each procedure will be performed solely for research purposes (meaning that the participant would not undergo the same number of procedures or would not undergo the procedure(s) at the same frequency if they were not participating in the study)	Risks If you are requesting a Waiver of Informed Consent, complete the table below. List the reasonably expected risks for each procedure or group of procedures under the following categories as appropriate: 
 • Serious and likely; • Serious and less likely; • Serious and rare; • Not serious and likely; • Not serious and less likely
1	Screening for Eligibility in Medical Records	N/A	Multiple Times	Breach of confidentiality; not serious and less likely
	Insert procedure here			
	Insert procedure here			
	Insert procedure here			
2	CRU visit			
	Screening Procedures	N/A	Once	N/A-See risks in the consent form
	Urine samples	N/A	Multiple times	N/A-See risks in the consent form
	10 mL blood draw		Once	N/A-See risks in the consent form
3	Post-CRU visit follow-up			
	Call patient to assess whether they were hospitalized in 7 days post discharge	N/A	Once	N/A-See risks in the consent form
	Insert procedure here			
	Insert procedure here			
4	Insert component 4 here			
	Insert procedure here			
	Insert procedure here			
	Insert procedure here			

5. Safety Precautions. (Describe safeguards to address the serious risks listed above.)

a. Describe the procedures for protecting against or minimizing any potential risks for each of the more than minimal risk research procedures listed above.

Risks and side effects related to Furoscix include those which are:

Likely, some may be Serious

In 100 people, approximately 21-100 may have:

- Dehydration
- Electrolyte depletion, including low potassium (hypokalemia), low sodium (hyponatremia), low magnesium (hypomagnesemia), low calcium (hypocalcemia).
- Dry mouth
- Thirst

Form A

IRB #

STU-2022-0768

- Weakness
- Muscle pains or cramps
- Low blood pressure
- High heart rate
- Arrhythmia
- Nausea or vomiting

Less Likely, some may be Serious

In 100 people, approximately 2-20 may have:

- Deterioration in kidney function
- Increased uric acid and gout
- Urine bladder spasm
- Transient injection site pain
- Fever
- Restlessness

Rare and Serious

In 100 people, approximately 1 or less may have:

- Exacerbation of systemic lupus erythematosus
- Allergy to furosemide/Systemic hypersensitivity reactions
- Liver or kidney damage
- Tinnitus and hearing loss
- Aplastic anemia, thrombocytopenia, agranulocytosis
- Skin hypersensitivity reactions

Risks and side effects related to Oral Diuretic Therapy:

Likely, some may be Serious

In 100 people, approximately 21-100 may have:

- Dehydration
- Electrolyte depletion, including low potassium (hypokalemia), low sodium (hyponatremia), low magnesium (hypomagnesemia), low calcium (hypocalcemia).
- Dry mouth
- Thirst
- Weakness
- Muscle pains or cramps
- Low blood pressure
- High heart rate
- Dizziness

Less Likely, some may be Serious

In 100 people, approximately 2-20 may have:

- Deterioration in kidney function or an acute kidney injury
- Increased uric acid and gout
- Urine bladder spasm

Rare and Serious

In 100 people, approximately 1 or less may have:

- Exacerbation of systemic lupus erythematosus
- Allergy to furosemide or torsemide/Systemic hypersensitivity reactions
- Liver or kidney damage
- Tinnitus and hearing loss
- Aplastic anemia (bone marrow failure), thrombocytopenia (low blood platelet count), agranulocytosis (low white blood cell count)
- Skin hypersensitivity reactions such as skin rash

Form A

IRB #

STU-2022-0768

Furoscix is a specific subcutaneous formulation of furosemide. Patients are required to be taking home diuretics as eligibility criteria; therefore we anticipate very few side effects associated with the medication. Skin reactions may occur with administration of Furoscix, although this is a rare side effect. Patients will be monitored for 8 hours post medication administration, with a serum potassium check performed after the study visit to ensure stable serum electrolytes.

b. Where appropriate, discuss provisions for ensuring necessary medical or professional intervention in the event of adverse events, or unanticipated problems involving subjects.

A physician will be always available during the study visits. A research nurse will be monitoring the patient throughout the research visit. We will also follow up with patients over the phone in a week after their study visit.

Should any AE's occur, it will be documented and medical care will be provided. The team will follow patient's AE until resolution. See Form D for more information.

c. Will the safeguards be different between/among groups?

Yes

No

N/A

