STUDY PROTOCOL AND STATISTICAL ANALYSIS PLAN

Official title: Furoscix in Heart Failure Patients with Diuretic Resistance

NCT number: NCT05528588

IRB Approved date: 07-22-24

Form A

IRB #

STU-2022-0768

PROTOCOL FORM / RESEARCH DESCRIPTION

If an item does not apply to your research project, indicate that the question is "**not applicable**" – do not leave sections blank

Click once on the highlighted entry in each box to provide your response. Click the item number/letter or word, if hyperlinked, for detailed instructions for that question. If your response requires inserting a table, picture, etc, you may need to first delete the box that surrounds the answer and then insert your table or other special document.

1. Purpose and objectives. *List the purpose and objectives:*

The purpose of this study is to assess the diuretic efficiency of subcutaneous furosemide (Furoscix) compared to oral diuretic therapy for patients post heart failure (HF) hospitalization and evaluate the impact of diuretic resistance as identified by the BAN-ADHF (Blood urea nitrogen, creatinine, Natriuretic Peptide levels, Atrial fibrillation, Diastolic blood pressure, Hypertension and Home diuretic dose, and Heart Failure hospitalization) risk score.

Key Outcomes:

1. Post-treatment urine output over 8 hours. This will be assessed in mL per mg of treatment (Furoscix vs. oral diuretic).
2. Post-treatment urine sodium. Urine sodium will be assessed hourly over 8 hours post-treatment.

Safety Outcome Measures:

1. Number of participants with post-intervention need for emergency department visit or hospitalization. The count of participants with post-intervention need for emergency department visit or hospitalization for worsening heart failure is assessed.

Goals: Successful completion of this project will establish proof of concept that Furoscix provides more effective post-hospitalization diuresis than the traditional oral dose in a diuretic resistance patient population. This study will provide pilot data to guide the design of larger studies involving a diuretic-resistant heart failure population.

2. Background.

- Describe past experimental and/or clinical findings leading to the formulation of your study.
- For research involving investigational drugs, describe the previously conducted animal and human studies.
- For research that involves FDA approved drugs or devices, describe the FDA approved uses of this drug/device in relation to your protocol.

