- Attach a copy of the approved labeling as a product package insert or from the Physician's Desk Reference.

You may reference sponsor's full protocol or grant application (section number and/or title) or if none, ensure background includes references.

Please respond to all components of this item, or clearly indicate which components are not applicable.

a. Background

Form A

IRB #

STU-2022-0768

Introduction

Heart failure is one of the leading causes of hospitalization in the United States, contributing to over 1 million emergency department visits and nearly 1 million hospitalizations for HF annually.¹ The estimated mean cost for HF was \$11,552 in 2014, totaling an estimated \$11 billion.² Thus, strategies to reduce the burden of acute care use for patients with heart failure are necessary. Acute decompensation of heart failure is characterized by volume overload and is primarily treated with intravenous diuretics. However, inefficient and ineffective diuresis both during hospitalization and in the post-discharge environment predispose patients to frequent readmission and a worse prognosis.³ Importantly, there is heterogeneity in patient response to intravenous diuresis, with an estimated 20-50% of patients having poor response to initial IV diuretic therapy.³ Patients who are resistant to intravenous diuresis have increased risk of re-hospitalization and mortality. Importantly, our group recently derived an integer-based risk score (BAN-ADHF score) to predict patients with low diuretic efficiency, with the research winning the NHLBI Heart Failure Data Challenge.^{4,5}

As part of patient's standard of care, they receive oral diuretics, including furosemide or torsemide, which are FDA approved for treating congestion and volume overload from heart failure. However, some patients are "resistant" to oral diuretics and have higher risk of repeat hospitalization. Therefore, purpose of this study is to evaluate treatment with subcutaneous furosemide (Furoscix) compared with oral diuretic therapy for patients with recent heart failure hospitalization either with or without diuretic resistance.

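### Randomisation is stratified by BAN-ADHF score and the purpose covers diuretic resistance, but the Statistical Analysis never uses the strata, so no result for resistant patients is planned.

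*Combined protocol and SAP*

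**What the plan says.** Section 1 (Purpose and objectives) has two parts. The first compares Furoscix with oral diuretic; the second is to "evaluate the impact of diuretic resistance as identified by the BAN-ADHF" score. The Goals paragraph looks for proof of concept of "more effective post-hospitalization diuresis than the traditional oral dose in a diuretic resistance patient population". The Introduction (section 2.a) describes the population as "patients with recent heart failure hospitalization either with or without diuretic resistance", and section 4.a plans 70 patients, with resistance defined as a score of 12 or more.

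Under Randomization in section 4.a, patients who consent and remain eligible reach the step where "they will undergo stratified randomization based on BAN-ADHF score", cut at 12. It continues: "Within each stratum, patients will be randomized in a 1:1 ratio".

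The Statistical Analysis in section 4.a makes two comparative statements. For urine output: "Differences in total urine produced will be compared between Furoscix versus oral diuretic groups". For sodium: "The urine sodium will be assessed hourly, and will be compared across the two groups". Resistance appears there only in the closing remark that the trial will be a "precursor for a larger, multicenter trial of Furoscix in patients with diuretic resistance". No other section supplies a stratum analysis, and the Key Outcomes in section 1 are not split by stratum.

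**The concern.** The design creates a randomised comparison inside each BAN-ADHF stratum, and the analysis text then does not use it. Two consequences follow.

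- **No estimate for the target population.** Followed as written, the plan gives one pooled arm difference over patients with and without resistance. No quota per stratum is set, so that difference could come mostly from patients scoring below 12. It cannot show whether the effect holds at 12 or above, which is the population named in the goal and in the planned larger trial. A resistant-patient result added later would be post hoc.
- **Some loss in the overall comparison.** If the stratum predicts urine output or sodium, leaving it out loses power. If allocation is also blocked within strata, the unadjusted standard error is slightly too large. That error is conservative and does not create false positives.

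**Working it through.** The plan has no figure to reproduce: 70 is a convenience sample, with no alpha, power, effect size or SD. The sizes below assume a two-sided 5% level, outcomes in units of the within-stratum SD, and a resistant share s of 20%, 50% or 70% (14, 35 or 49 of 70). The only nearby figure in the documents is 20-50% with poor response to initial IV diuretic (section 2.a), which is not the share scoring 12 or more.

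**(a) Overall comparison if the stratum is ignored.** Let the strata differ by d SD, with s = 0.5 and allocation balanced within strata.

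- Variance explained: R² = s(1−s)d² / (1 + s(1−s)d²). For d = 0.5: 0.0625/1.0625 = 0.059. For d = 1.0: 0.25/1.25 = 0.20.
- Effective critical value: 1.96/√(1−R²) = 2.02 and 2.19.
- True alpha: 2[1 − Φ(2.02)] = 0.043 and 2[1 − Φ(2.19)] = 0.028.
- Power when the adjusted test has 80%: Φ(2.80 − 2.02) = 0.78 and Φ(2.80 − 2.19) = 0.73.

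A simulation with N = 70, 20,000 runs and a true effect of 0.68 SD agrees. With blocks of 4, unadjusted alpha is 4.4% and 2.9%, and power is 79% and 73% against 80% adjusted. Without blocking, alpha stays near 5% and power is 77% and 70% against 79% adjusted.

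**(b) Precision in the resistant stratum.** Half-width = t × √(1/n₁ + 1/n₂), with t on n₁ + n₂ − 2 df.

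| Patients | Split | t | √(1/n₁ + 1/n₂) | Half-width (SD) |
|---|---|---|---|---|
| 14 (20%) | 7 + 7 | 2.179 | 0.535 | 1.16 |
| 35 (50%) | 17 + 18 | 2.035 | 0.338 | 0.69 |
| 49 (70%) | 24 + 25 | 2.012 | 0.286 | 0.57 |
| All 70 | 35 + 35 | 1.995 | 0.239 | 0.48 |

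Taking the residual variance from a model on all 70 patients (66 df) lowers the first row to about 1.07 SD and barely changes the others.

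**(c) Treatment-by-stratum contrast.** SE = √(sum of 1/n over the four arm-by-stratum cells); power comes from the noncentral t with 66 df.

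| Share | Cells | SE | Detectable at 80% power (SD) | Power for 0.67 SD |
|---|---|---|---|---|
| 20% | 7, 7, 28, 28 | 0.598 | 1.70 | 20% |
| 50% | 17, 18, 17, 18 | 0.478 | 1.36 | 28% |
| 70% | 24, 25, 10, 11 | 0.522 | 1.48 | 24% |

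The normal approximation, 2.80 × SE, gives 1.67, 1.34 and 1.46 SD. The reference value of 0.67 SD is what 35 per arm detects overall with 80% power: 2.80 × √(2/35) = 0.67.

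**The case against.** The best case for the plan is that silence is not a decision. The purpose declares the interest in resistance, patients without adequate score data are excluded, and allocation is 1:1 within each stratum, so the estimate can be produced later. The Statistical Analysis names no test or model for any outcome, so part (a) describes a hypothetical unadjusted test. Its upper end needs a 1.0 SD gap between strata, and its alpha effect needs blocking; the documents support neither. The study is a pilot with a convenience sample, its main comparison is valid, and a contrast with 20-28% power tells little. The aim also does not say whether the impact of resistance means prognosis, the effect within a stratum, or an interaction.

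Much of this stands. The main comparison is unharmed in validity, part (a) is modest and conditional, and the 70% share is only illustrative. None of it supplies the missing analysis. Stratified allocation balances the arms; it does not define an estimate. The ambiguity of the aim is a further reason to write the analysis down. Low power argues for labelling the stratum results exploratory and showing their intervals, not for leaving out the population named in the goal.

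**Conclusion.** The concern holds. A stated objective, and the population in the stated goal, have no specified analysis, although randomisation was built around exactly that split. This is more than missing detail: the plan carried out as written yields no estimate for patients scoring 12 or more.

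The loss of that estimate carries the weight. The cost to the overall comparison is secondary: about 1 to 7 points of power with blocked allocation and 2 to 9 without, for strata differing by 0.5 to 1.0 SD, with no inflation of false positives. The stratum results will be imprecise at any plausible share. The textual finding needs no assumption; every size depends on the assumed share, stratum gap, alpha and power. It should be corrected, but it does not threaten the main comparison.

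**What to change.** Amend the Statistical Analysis in section 4.a as follows.

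1. Analyse each declared outcome with a linear model containing arm and BAN-ADHF stratum (12 or more versus below 12), and include the stratum in whatever model is used for hourly urine sodium.
2. Report, labelled exploratory, the arm difference with 95% CI in each stratum and the treatment-by-stratum contrast with its CI. Base any statement about resistant patients on the estimate from the stratum scoring 12 or more.
3. State in advance that these estimates will be imprecise, using the ranges above. Otherwise, reword the goal to cover recently discharged patients with and without diuretic resistance.

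One caution: home diuretic dose is a component of the score and also sets the control arm's mL/mg denominator, so a stratum contrast in mL/mg can be distorted. Show the stratum results for total 8-hour urine volume alongside the declared mL/mg outcome, not in its place.

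The cost is wording in one section. No new patients or data are needed, because total volume is already measured and inadequate score data is an exclusion. The downside is that the stratum intervals will be visibly wide.

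### Patients are told to withhold their home diuretic before consent and final eligibility, so some may delay or miss a dose for a trial they never enter

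*Combined protocol and SAP*

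**What the plan says.** Under Randomization in section 4.a, the instruction to withhold treatment is given by telephone before the visit: "Patients will be informed via telephone prior to visit to not take home oral dose of diuretic on the day of the visit". The same sentence extends the restriction to caffeine and to other drugs that might raise urine output that day.

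The steps that decide whether someone enters the trial are placed at the visit. The last bullet under Screening reads: "At the research appointment, patients will be asked if they are interested in voluntarily participating in this study". The Pre-Randomization list for the research visit then has "Confirm eligibility" and "Obtain informed consent", followed by the physical examination with vital signs and the medication review. Entry depends on both: "If patients still meet all eligibility criteria and sign informed consent, they will undergo stratified randomization".

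The one waiver requested in this form concerns records: "We are requesting a partial HIPAA waiver to review electronic health records and confirm their eligibility in the study".

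Under the control arm, patients bring their own diuretic and take it during the visit, and the investigational pharmacy supplies an equivalent if they did not bring it. The supplied text has no matching provision for someone who attends and is not randomised. The withholding step appears neither in table 4.d, which together with table 4.b is meant to account for every research procedure, nor in the safety precautions of section 5.

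**The concern.** Withholding a prescribed diuretic for the sake of a measurement is something the study does to the patient. Here it is asked of people who have at most expressed interest, before they have consented and before eligibility is settled. They are no more than 14 days past discharge for decompensated heart failure, and ideally 1 to 7 days. The Background itself links ineffective diuresis after discharge to readmission and a worse prognosis, and one randomisation stratum is defined by predicted diuretic resistance.

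What is at stake is consent and patient safety for those who withhold the dose and then do not enter. They would have changed their treatment for a study they are not in, and the supplied text does not say what happens next.

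**Working it through.** The plan states no figure on this point, so there is none to reproduce. The sample size of 70 is a convenience sample. The check is mainly one of order.

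**Order of events, from section 4.a**

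| Step | When | Heading |
|---|---|---|
| Record review, BAN-ADHF score | Before visit | Screening |
| Approach; interested patients scheduled | Before visit | Screening |
| Telephone instruction to withhold the diuretic | Before visit | Randomization |
| Asked about voluntary participation | At visit | Screening, last bullet |
| Eligibility confirmed, consent obtained, vital signs and medications reviewed | At visit | Pre-Randomization |
| Randomised if still eligible and consented | At visit | Randomization |

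The instruction therefore precedes the participation question, the consent and the final eligibility check. No supplied section describes an earlier agreement to withhold the dose. The condition attached to randomisation shows that the plan itself foresees some attendees not entering.

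**Size, under an assumption**

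Inputs: 70 to be randomised (section 4.a, Statistical Analysis); f, the share of attendees not randomised, which is *assumed* because the documents give no value. I also assume that every attendee followed the telephone instruction.

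- Expected non-entrants by the time 70 are randomised = 70 × f / (1 − f)
- Chance of at least one = 1 − (1 − f)^70

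| Assumed f | Expected non-entrants | Chance of at least one |
|---|---|---|
| 1% | 70 × 0.01 / 0.99 = 0.7 | 51% |
| 2% | 70 × 0.02 / 0.98 = 1.4 | 76% |
| 5% | 70 × 0.05 / 0.95 = 3.7 | 97% |
| 10% | 70 × 0.10 / 0.90 = 7.8 | 99.9% |
| 20% | 70 × 0.20 / 0.80 = 17.5 | about 100% |

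The range is about 1 to 18 people. It restates the assumption and is not evidence of a rate. It does show that even at 2% at least one such patient is more likely than not.

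**The case against.** The case on the other side has real force on how much harm follows, and less on the order of events.

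- **A reader might infer that patients will skip a dose.** The documents do not support that. The instruction covers the day of the visit only. Patients in the control arm bring their own diuretic, and since the arm is unknown beforehand, presumably all are told to bring it. Someone who declines may well have the drug in hand the same day, and nothing in the plan bars taking it. A delayed or possibly missed dose is as far as the text goes.
- **Non-entry should be uncommon.** Criteria are checked in the record, and only interested patients are scheduled. Many exclusions are facts already in the chart. This lowers the number but does not rule out late refusal or a late finding. The criterion "Systolic blood pressure <100" is a plausible example because vital signs are taken at the visit, but no time point is attached to it, so its use on visit-day readings is an inference.
- **Visits are staffed.** Section 5 has a physician available and a research nurse monitoring. That helps anyone present, but it is not a plan for those who are not randomised.
- **Other documents may cover it.** Consent pages were removed, and Form D, cited for adverse events, is not supplied. Either might address non-entrants, so that gap can only be stated for the supplied text. A form signed at the visit would still come after the withholding it was meant to authorise.
- **A reader might infer that the sections contradict each other.** They do not: Screening, Pre-Randomization and Randomization together give one consistent order. The concern is with that order.
- **A reader might infer bias in the treatment comparison.** The withholding precedes randomisation and applies to both arms alike, so the comparison is not affected.

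**Conclusion.** The point holds as a matter of consent and patient safety. As written, the plan asks patients to change their treatment before they have consented and before eligibility is final, and it expects that some may not go on to be randomised. Those patients may have delayed or missed one day's dose, and the supplied text makes no provision for them.

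The number affected cannot be taken from the documents; about 1 to 18 rests wholly on the assumed 1% to 20%, and the low end is as admissible as the high end. The finding needs no particular rate, because the order of steps is explicit. Its weight is that of a cheap improvement worth making: the exposure is short and partly mitigated, and neither the sample size nor the between-arm comparison changes.

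**What to change.** Change the order in section 4.a so that informed consent is obtained, for example by telephone or electronically, before the instruction to withhold the diuretic is given. Reconfirm eligibility and consent at the visit, as the Pre-Randomization list already provides. List the withholding step as a research procedure in table 4.d.

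The investigators should also state their own plan for patients who withheld a dose but are not randomised. That is a clinical decision for them, and no rule is proposed here.

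The cost is a protocol amendment, an earlier consent step, and consent time spent on some patients who never attend. The design, randomisation and analysis stay as they are.
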